2.1.2 Secondary objective

To assess immunologic/molecular responses to tremelimumab and durvalumab in patients with HR+/HER2- breast cancer who receive the combination therapy.

2.1.3 Exploratory objective

To evaluate the pathologic response in patients with HR+/HER2- breast cancer receiving tremelimumab plus durvalumab prior to initiating standard neoadjuvant chemotherapy.

3. STUDY DESIGN

3.1 Overview of study design

This is an open-label, single-arm, presurgical pilot study in patients with HR+/HER2- breast cancer.

[figure not shown]
There will be 15 patients enrolled.

Patients will receive durvalumab at 1500 mg plus tremelimumab at 75 mg every 4 weeks for a total of 2 doses. A standard regimen of neoadjuvant chemotherapy will be initiated within 4 weeks after the last infusion of durvalumab and tremelimumab. A biopsy will be obtained after the last infusion of durvalumab and tremelimumab before neoadjuvant chemotherapy is started.

Patients will undergo surgery after the completion of standard neoadjuvant chemotherapy.

3.2 Study schema

Figure 1. Study Schema

Notes:

- A. Eligible patients include those with HR+/HER2- breast cancer, clinical stage II-III, planned for neoadjuvant chemotherapy.
- B. The first day of dosing is considered Day 1. Tremelimumab will be administered first. The duration of tremelimumab infusion will be 1 hour. Durvalumab infusion will start approximately 1 hour after the end of the tremelimumab infusion. The duration of durvalumab infusion will be 1 hour.
- C. Neoadjuvant systemic therapy will begin within 28 days of the last infusion of tremelimumab and durvalumab.
- D. Surgery will be performed within 8 weeks of completing neoadjuvant systemic therapy.

3.3 Study Oversight for Safety Evaluation

The study would be stopped if an unacceptable number of patients experience an extreme toxicity (ETOX). For trial monitoring, a patient will be determined to have an ETOX if either condition is met:

- The patient experiences any grade 3 or higher adverse event (AE) that is possibly, probably, or definitely related to therapy (durvalumab + tremelimumab) received on this protocol and occurs up to 90 days after the last dose of therapy. As an exception, any such AE that is potentially treatable with steroids will only count as an ETOX if it does not improve to grade 1 or better within 2 weeks.

- The patient has a delay in initiation of neoadjuvant systemic therapy of 6 weeks or more due to AE, even if that AE does not meet the definition of ETOX.

Based on the method of Thall (Thall et al 1995), we will monitor ETOX continually after the 5th patient receives treatment. We assume $\Theta_T \sim \text{beta}(0.20, 0.8)$ for the current study, where Θ_T is the probability of a patient experiencing an ETOX. Our stopping rule is given by the following probability statement: $P_T(\Theta_T > 0.20 \mid \text{data}) > 0.90$. That is, we will stop the trial if, at any time during the study, we determine that there is more than a 90% chance that the ETOX rate is more than 20%.

The stopping boundaries for this toxicity rule are to terminate the trial if the number of patients with ETOX compared to the number of patients on trial exceed the limits in table 1, with operating characteristics for this rule in table 2. After 5 patients, this table will be consulted prior to enrolling each patient. Enrollment will not require waiting for complete information for the previous patient, unless an ETOX in that patient would result in hitting the stopping rule.

Table 1. Stopping Criteria for Excessive Toxicities Based on ETOX

If there are this many patients with ETOX	3	4	5	6 or more
Stop if this many patients (or fewer) have been evaluated at least once for toxicity	6	10	13	15*

* The trial will stop at 15 patients, but if 6 or more patients experience ETOX, this regimen will be too toxic for further study in this population.

Table 2. Operating Characteristics for Toxicity Monitoring

True ETOX rate	Probability of Stopping Early	Median (25 th %ile, 75 th %ile)	Average Number of Patients	Average Number of Patients with ETOX
0.05	0.003	15 (15, 15)	15.0	0.75
0.10	0.02	15 (15, 15)	14.8	1.5
0.20	0.17	15 (15, 15)	13.7	2.7
0.30	0.45	15 (6, 15)	11.6	3.5
0.40	0.72	8 (5, 15)	9.3	3.7

4. PATIENT SELECTION, ENROLLMENT, RANDOMIZATION, RESTRICTIONS, DISCONTINUATION AND WITHDRAWAL

Each patient must meet all of the inclusion criteria (Section 4.1) and none of the exclusion criteria (Section 4.2) for this study.

4.1 Inclusion criteria

For inclusion in the study, patients should fulfill the following criteria:

1. Written informed consent and any locally-required authorization (e.g., HIPAA) obtained from the subject prior to performing any protocol-related procedures, including screening evaluations
2. Age \geq 18 years at time of study entry
3. Eastern Cooperative Oncology Group (ECOG) performance status of 0 or 1
4. Hormone receptor positive (defined as estrogen receptor [ER] and/or progesterone receptor [PR] positive), HER2 negative breast cancer that is clinically staged II-III with no known metastatic disease. ER and/or PR defined as positive if expression $>10\%$ by immunohistochemistry (IHC). HER2 negative or non-amplified as determined by the current ASCO-CAP criteria which are as follows: HER2 testing by IHC as 0 or 1+. If HER2 is 2+, ISH (in situ hybridization) must be performed. HER2 is positive if:
 - IHC 3+ based on circumferential membrane staining that is
 - complete, intense
 - ISH positive based on:
 - Single-probe average HER2 copy number ≥ 6.0 signals/cell.
 - Dual-probe HER2/CEP17 ratio ≥ 2.0 ;c,e with an average HER2 copy number ≥ 4.0 signals/cell
 - Dual-probe HER2/CEP17 ratio ≥ 2.0 ;c,e with an average HER2 copy number < 4.0 signals/cell
 - Dual-probe HER2/CEP17 ratio < 2.0 ;c,e with an average HER2 copy number ≥ 6.0 signals/cell
5. Chemotherapy is planned for the patient in the neoadjuvant setting
6. Adequate normal organ and marrow function as defined below:
 - Haemoglobin ≥ 9.0 g/dL
 - Absolute neutrophil count (ANC) $\geq 1.5 \times 10^9/L$ (≥ 1500 per mm^3)
 - Platelet count $\geq 100 \times 10^9/L$ ($\geq 100,000$ per mm^3)

- Serum bilirubin $\leq 1.5 \times$ institutional upper limit of normal (ULN). This will not apply to subjects with confirmed Gilbert's syndrome (persistent or recurrent hyperbilirubinemia that is predominantly unconjugated in the absence of hemolysis or hepatic pathology), who will be allowed only upon treating physician, Principle Principal Investigators (PI) or co-PI approval.
- AST (SGOT)/ALT (SGPT) $\leq 2.5 \times$ institutional upper limit of normal unless liver metastases are present, in which case it must be $\leq 5 \times$ ULN
- Creatinine CL > 40 mL/min by the Cockcroft-Gault formula (Cockcroft and Gault 1976) or by 24-hour urine collection for determination of creatinine clearance:

Males:

$$\text{Creatinine CL (mL/min)} = \frac{\text{Weight (kg)} \times (140 - \text{Age})}{72 \times \text{serum creatinine (mg/dL)}}$$

Females:

$$\text{Creatinine CL (mL/min)} = \frac{\text{Weight (kg)} \times (140 - \text{Age})}{72 \times \text{serum creatinine (mg/dL)}} \times 0.85$$

7. Female subjects must either be of non-reproductive potential (ie, post-menopausal by history: ≥ 60 years old and no menses for ≥ 1 year without an alternative medical cause; OR history of hysterectomy, OR history of bilateral tubal ligation, OR history of bilateral oophorectomy) or must have a negative urine pregnancy test upon study entry
8. Subject is willing and able to comply with the protocol for the duration of the study including undergoing treatment and scheduled visits and examinations including follow up

4.2 Exclusion criteria

Subjects should not enter the study if any of the following exclusion criteria are fulfilled:

1. Involvement in the planning and/or conduct of the study (applies to both AstraZeneca staff and/or staff at the study site)
2. Participation in another clinical study with an investigational product during the last 1 month prior to initiation of therapy
3. Any previous treatment with a PD1 or PD-L1 inhibitor, including durvalumab or an anti-CTLA4, including tremelimumab
4. History of another primary malignancy except for:

- Malignancy treated with curative intent and with no known active disease ≥ 5 years before the first dose of study drug and of low potential risk for recurrence
 - Adequately treated non-melanoma skin cancer or lentigo maligna without evidence of disease
 - Adequately treated carcinoma in situ without evidence of disease eg, cervical cancer in situ
5. Has received therapy for this current diagnosis of breast cancer including endocrine therapy or chemotherapy
 6. A single QT interval corrected for heart rate (QTc) ≥ 470 . If an ECG is interpreted to be a prolonged QT interval, 2 additional ECGs will be obtained and the PI will then evaluate all 3 ECGs to determine whether the patient should be excluded. Mean QT interval corrected for heart rate (QTc) ≥ 470 ms calculated from 3 electrocardiograms (ECGs) using Fredericia's Correction
 7. Current or prior use of immunosuppressive medication within 28 days before the first dose of durvalumab or tremelimumab, with the exceptions of intranasal and inhaled corticosteroids or systemic corticosteroids at physiological doses, which are not to exceed 10 mg/day of prednisone, or an equivalent corticosteroid
 8. Active or prior documented autoimmune disease within the past 2 years NOTE: Subjects with vitiligo, Grave's disease, or psoriasis not requiring systemic treatment (within the past 2 years) are not excluded.
 9. Active or prior documented inflammatory bowel disease (e.g., Crohn's disease, ulcerative colitis)
 10. History of primary immunodeficiency
 11. History of allogeneic organ transplant
 12. History of hypersensitivity to durvalumab or tremelimumab or any excipient
 13. History of hypersensitivity to the combination or comparator agent (if applicable)
 14. Uncontrolled intercurrent illness including, but not limited to, ongoing or active infection, symptomatic congestive heart failure, uncontrolled hypertension, unstable angina pectoris, cardiac arrhythmia, active peptic ulcer disease or gastritis, active bleeding diatheses including any subject known to have evidence of acute or chronic hepatitis B, hepatitis C or human immunodeficiency virus (HIV), or psychiatric illness/social situations that would limit compliance with study requirements or compromise the ability of the subject to give written informed consent
 15. Known history of previous clinical diagnosis of tuberculosis
 16. History of leptomeningeal carcinomatosis

17. Receipt of live attenuated vaccination within 30 days prior to study entry or within 30 days of receiving durvalumab or tremelimumab
18. Female subjects who are pregnant, breast-feeding or male or female patients of reproductive potential who are not employing an effective method of birth control
19. Any condition that, in the opinion of the investigator, would interfere with evaluation of study treatment or interpretation of patient safety or study results
20. Subjects with uncontrolled seizures

4.3 Withdrawal of Subjects from Study Treatment and/or Study

Permanent discontinuation of study treatment with durvalumab and tremelimumab

An individual subject will not receive any further investigational product if any of the following occur in the subject in question:

1. Withdrawal of consent or lost to follow-up
2. Adverse event that, in the opinion of the investigator or AstraZeneca/MedImmune, contraindicates further dosing
3. Subject is determined to have met one or more of the exclusion criteria for study participation at study entry and continuing investigational therapy might constitute a safety risk
4. Pregnancy or intent to become pregnant
5. Any AE that meets criteria for discontinuation as defined in Section 10.3
6. Grade ≥ 3 infusion reaction
7. Subject noncompliance that, in the opinion of the investigator or AstraZeneca/MedImmune, warrants withdrawal; eg, refusal to adhere to scheduled visits
8. Initiation of alternative anticancer therapy including another investigational agent
9. Confirmation of PD and investigator determination that the subject is no longer benefiting from treatment with durvalumab + tremelimumab

Subjects who are permanently discontinued from further receipt of investigational product, regardless of the reason (withdrawal of consent, due to an AE, other), will be identified as having permanently discontinued treatment.

Subjects who are permanently discontinued from receiving investigational product will be

followed for safety, including the collection of any protocol-specified blood specimens, unless consent is withdrawn or the subject is lost to follow-up or enrolled in another clinical study.

Withdrawal of consent

If consent is withdrawn, the subject will not receive any further investigational product or further study observation.

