10.3.1 Study recording period and follow-up for adverse events and serious adverse events

Adverse events and serious adverse events will be recorded from time of first protocol intervention, throughout the treatment period and including the follow-up period (90 +/-7 days after the last dose of durvalumab + tremelimumab).

During the course of the study all AEs and SAEs should be proactively followed up for each subject. Every effort should be made to obtain a resolution for all events, even if the events continue after discontinuation/study completion.

If a subject discontinues from treatment for reasons other than disease progression, and therefore continues to have tumor assessments, drug or procedure-related SAEs must be captured until the patient is considered to have confirmed PD and will have no further tumor assessments.

The investigator is responsible for following all SAEs until resolution, until the subject returns to baseline status, or until the condition has stabilized with the expectation that it will remain chronic, even if this extends beyond study participation.

Follow-up of unresolved adverse events

Any AEs that are unresolved at the subject's last visit (90 days post End of Treatment) in the study are followed up by the investigator for as long as medically indicated, but without further recording. After 90 days, only subjects with ongoing investigational product-related SAEs will continue to be followed for safety.

AstraZeneca/MedImmune and the IND Office retain the right to request additional information for any subject with ongoing AE(s)/SAE(s) at the end of the study, if judged necessary.

Post study events

After the subject has been permanently withdrawn from the study, there is no obligation for the investigator to actively report information on new AE or SAEs occurring in former study subjects after the 90-day safety follow-up period for patients treated with durvalumab + tremelimumab. However, if an investigator learns of any SAEs, including death, at any time after the subject has been permanently withdrawn from study, and he/she considers there is a reasonable possibility that the event is related to study treatment, the investigator should notify the study The University of Texas MD Anderson Cancer Center and AstraZeneca/MedImmune Drug Safety.

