11. STATISTICAL METHODS AND SAMPLE SIZE DETERMINATION

11.1 Description of analysis sets

11.1.1 Safety analysis set

All patients who receive at least one dose of study drug will be included in the safety monitoring and safety analysis.

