11.5 Interim Analysis: Safety Monitoring

Any patient who received the first dose of study medication will be included in the ongoing safety monitoring. For trial monitoring and decisions about future trials, a patient will be determined to have an extreme toxicity (ETOX) if either condition is met:

- The patient experiences any grade 3 or higher adverse event (AE) that is possibly, probably, or definitely related to therapy received on this protocol and occurs up to 90 days after the last dose of therapy (durvalumab + tremelimumab). As an exception, any such AE that is potentially treatable with steroids will only count as an ETOX if it does not improve to grade 1 or better within 2 weeks.
- The patient has a delay in surgery of 6 weeks or more due to AE, even if that AE does not meet the definition of ETOX.

Based on the method of Thall (1995)⁹, we will monitor ETOX **continually after the 5th patient** receives treatment. Continuous monitoring will occur monthly. We assume $\Theta_T \sim \text{beta}(0.20, 0.8)$ for the current study, where Θ_T is the probability of a patient experiencing an ETOX. Our stopping rule is given by the following probability statement: $P_T(\Theta_T > 0.20 \mid \text{data}) > 0.90$. That is, we will stop the trial if, at any time during the study, we determine that there is more than a 90% chance that the ETOX rate is more than 20%.

The stopping boundaries for this toxicity rule are to terminate the trial if the number of patients with ETOX compared to the number of patients on trial exceed the limits in table 1, with

operating characteristics for this rule in table 2. After 5 patients, this table will be consulted prior to enrolling each patient. Enrollment will not require waiting for complete information for the previous patient, unless an ETOX in that patient would result in hitting the stopping rule. Boundaries and operating characteristics were calculated in Multic Lean v2.1.

Table 1. Stopping Criteria for Excessive Toxicities Based on ETOX

If there are this many patients with ETOX	3	4	5	6 or more
Stop if this many patients (or fewer) have been evaluated at least once for toxicity	6	10	13	15*

* The trial will stop at 15 patients, but if 6 or more patients experience ETOX, this regimen will be too toxic for further study in this population.

Table 2. Operating Characteristics for Toxicity Monitoring

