11.6 Analysis Plan

Feasibility will be assessed according to the endpoint definition provided above. Additionally, the total number of patients screened to achieve 15 enrolled patients will be reported. Since it is not known whether durvalumab plus tremelimumab can be safely used in the presurgical setting in patients with HR+, HER2- breast cancer, our other primary endpoint is safety. Adverse events will be tabulated by CTCAE grade and ETOX status. A 95% credible interval will be presented for the ETOX rate among patients in the safety analysis set. Surgery delay will be reported with the numbers of patients with any delay, as well as the median, IQR, min

and max for delay times. If 6 or more patients experience ETOX, then this combination will be determined to be too toxic for these patients.

For blood and tumor measures, descriptive statistics including plots, tabulations, mean, median and standard deviations will be used to summarize data. Differences and/or percent changes will be calculated between pre- and post-therapy samples from each patient and described as continuous measures.

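### Section 4.3 ends safety follow-up when a discontinued patient joins another study, in conflict with the 90-day capture rules, and the ETOX analysis has no rule for incomplete windows

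*Combined protocol and SAP*

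**What the plan says.** **Who is counted.** Section 11.1.1: "All patients who receive at least one dose of study drug will be included in the safety monitoring and safety analysis". Section 11.5 repeats this for monitoring: "Any patient who received the first dose of study medication will be included in the ongoing safety monitoring". The row label of Table 1 asks only for one evaluation, not a complete window: "Stop if this many patients (or fewer) have been evaluated at least once for toxicity".

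**What is counted.** Under 11.5, "a patient will be determined to have an extreme toxicity (ETOX) if either condition is met". The adverse-event condition covers a qualifying event that "occurs up to 90 days after the last dose of therapy (durvalumab + tremelimumab". The status is yes or no; there is no category for a patient who cannot be evaluated.

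**How long patients are observed.** Three sections bear on this, and they differ:
- Section 4.3 follows permanently discontinued patients for safety "unless consent is withdrawn or the subject is lost to follow-up or enrolled in another clinical study".
- Section 10.3.1 records adverse events and serious adverse events through treatment, "including the follow-up period (90 +/-7 days after the last dose of durvalumab + tremelimumab"), with no exception for joining another study.
- Section 10.1.2 captures serious adverse events to 90 days after the last dose; withdrawal of consent is the only exception it names.

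**What is reported.** Section 11.6: "A 95% credible interval will be presented for the ETOX rate among patients in the safety analysis set". It also declares the combination too toxic at 6 or more ETOX. Neither 11.5 nor 11.6 says how a dosed patient with an incomplete 90-day window is handled.

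**The concern.** Safety is a co-primary endpoint, and its ETOX summary depends on knowing each dosed patient's status over the window. Section 4.3 allows collection to stop early for one group, discontinued patients who enter another study, although the other two sections would keep collecting. Its own list of reasons for discontinuation includes adverse events and the start of another investigational agent, so this group is foreseeable. Patients who withdraw consent or are lost also have incomplete windows, and no plan can prevent that.

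With a yes/no outcome and an all-dosed denominator, a patient with no ETOX recorded so far adds one to the denominator and nothing to the numerator. Any later, unseen ETOX is missed. The error runs in one direction, towards a lower rate, a lower credible interval, fewer stops under Table 1 and a smaller count against the threshold of 6. With 15 patients, one or two such cases can matter.

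**Working it through.** **Inputs from the plan.** Prior beta(0.2, 0.8); stop if P(rate > 0.20 | data) > 0.90, from patient 5; maximum 15 patients; too toxic at 6 or more ETOX (sections 11.4 to 11.6).

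**Formula.** With x ETOX among n patients the posterior is beta(0.2 + x, 0.8 + n − x). P(rate > 0.20) is its upper tail at 0.20, and the 95% credible interval is taken between its 2.5% and 97.5% points.

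**Step 1: reproduce the plan.** The smallest x that stops is 3 for n = 5–6, 4 for n = 7–10, 5 for n = 11–13 and 6 for n = 14–15, identical to Table 1. An exact binomial recursion with a look after each patient from 5 to 14 gives:

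| True ETOX rate | Probability of stopping early, recomputed | Table 2 |
|---|---|---|
| 0.05 | 0.0028 | 0.003 |
| 0.10 | 0.0239 | 0.02 |
| 0.20 | 0.1743 | 0.17 |
| 0.30 | 0.4492 | 0.45 |
| 0.40 | 0.7244 | 0.72 |

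Table 2 reproduces when every counted patient's ETOX status is treated as known.

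**Step 2: final analysis, assumed example.** Suppose 15 patients are dosed, 4 have an observed ETOX, and 2 others have no ETOX and an incomplete window.

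| Handling of the two | x/n | Rate | P(rate > 0.20) | 95% credible interval | 6-ETOX verdict |
|---|---|---|---|---|---|
| Counted as non-events (default) | 4/15 | 27% | 0.692 | 0.09–0.50 | not too toxic |
| Excluded | 4/13 | 31% | 0.786 | 0.10–0.55 | not too toxic |
| One had ETOX | 5/15 | 33% | 0.863 | 0.13–0.56 | not too toxic |
| Both had ETOX (worst case) | 6/15 | 40% | 0.951 | 0.17–0.63 | too toxic |

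The verdict changes only in the last row. If each of the two had ETOX independently at the 4/13 rate, that row would have probability (4/13)² = 16/169, about 0.09.

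**Step 3: monitoring near a boundary.** Keeping or dropping one patient who has no ETOX and an incomplete window moves P(rate > 0.20) across 0.90:
- 3/7 gives 0.886 (continue); 3/6 gives 0.927 (stop).
- 4/11 gives 0.869 (continue); 4/10 gives 0.904 (stop).
- 5/14 gives 0.893 (continue); 5/13 gives 0.920 (stop).

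**Step 4: effect on the stopping probability.** The documents give no loss rate, so assume that a share f of ETOX goes unseen and is counted as no ETOX. The effective rate is then p(1 − f).

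| True rate p | f = 0 | 1/15 | 2/15 | 1/5 | 1/3 |
|---|---|---|---|---|---|
| 0.20 | 0.174 | 0.145 | 0.119 | 0.095 | 0.056 |
| 0.30 | 0.449 | 0.390 | 0.331 | 0.275 | 0.174 |
| 0.40 | 0.724 | 0.658 | 0.586 | 0.509 | 0.351 |

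For example, at p = 0.40 and f = 2/15 the effective rate is 0.40 × 13/15 = 0.347, and the chance of stopping early falls from 0.724 to 0.586.

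**The case against.** A reader might infer that the plan scores every incompletely observed patient as free of toxicity. The documents do not say so. They are silent, and the non-event is what a yes/no outcome with an all-dosed denominator produces by default. Nor does every early leaver add a non-event: an ETOX recorded before departure counts, and some patients stopped for a related grade 3 or higher event will already be ETOX, subject to the steroid exception. Only later events in patients with none so far are at risk.

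Nor do the documents uniformly end capture when a patient joins another study. Sections 10.1.2 and 10.3.1 would continue, and 8.1.3 follows all subjects until breast surgery. This is a conflict between sections, not a settled rule. It still matters, because staff who follow 4.3 as written could stop collecting primary-endpoint data.

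The affected group is probably small: the 4.3 clause covers only permanently discontinued patients, in a single-centre trial of two doses four weeks apart whose patients go on to chemotherapy and surgery. Nothing in the documents shows that those who stop treatment early are the likeliest to be lost. The worked example is assumed, and its verdict flips only at the extreme.

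The all-dosed denominator is itself sound, since it keeps every observed event in the analysis. The rule in 11.5 on waiting for complete information does not fill the gap: it concerns the previous patient at an enrolment decision, not a patient who is never fully observed.

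**Conclusion.** The point holds in limited form. Section 4.3 contradicts 10.1.2 and 10.3.1 on patients who enter another study, and the ETOX analysis has no rule for incomplete windows. Following 4.3 as written can cut short the ascertainment of a co-primary endpoint, and the resulting bias is downward.

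Its size cannot be stated, because no loss rate is given. Under the assumed 4 ETOX and 2 incomplete windows among 15, P(rate > 0.20) runs from 0.69 to 0.95, and the 6-ETOX verdict changes only if both patients had ETOX. The stopping probabilities in Step 4 rest likewise on assumed shares of unseen events. This merits a correction to the text and a short sensitivity analysis; it does not show that the planned safety conclusion will be wrong.

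**What to change.** 1. **Section 4.3.** Reconcile it with 10.1.2 and 10.3.1: remove entry into another study as a reason to end adverse-event and ETOX collection before day 90 while consent stands.
2. **Section 11.6.** Keep all observed ETOX events. Report the number of dosed patients with no ETOX and an incomplete 90-day window. Repeat the rate and credible interval with those patients excluded, and add a worst-case bound that counts them as ETOX, stating whether the 6-or-more decision would change.

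Two details matter. Exclude only patients without an ETOX; dropping everyone with an incomplete window would discard observed toxicities. And exclusion informs the rate and interval only: it cannot alter a verdict based on a count, so the worst-case bound is the check on that decision.

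**Cost.** A deletion in 4.3, a few sentences in 11.6, and a chart or telephone check for a few patients. Events after another investigational agent will be harder to attribute, and the reported range may be less favourable. No additional patients are needed.
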